## **Phase II**

### **Specific Aim 2: To assess preliminary outcomes of ESTIMA**

**Recruitment and Random Assignment.** We will recruit ESTIMA participants from those who are completing 12 month follow-up for the parent study, using the same eligibility criteria and recruitment in Specific Aim 1 (assessing interest among those who indicate willingness to be recruited into a sub-study and based on responses in their surveys from the parent study), with an additional criteria related to women's drug use frequency; the specific criteria will be determined based on Aim 1 findings, consultation from the CAB and *Via* microfinance (drug use data will be retrieved from the parent survey; 41% and 53% of participants from the parent study report using drugs and alcohol less than once per week respectively). *Those who participated in Aim 1 and who fall within these eligibility criteria will be eligible for participation.* Research staff of the K01 and parent grant will work jointly to identify those willing and eligible during the 12 months follow-up data collection of the parent grant. From the parent study, we will recruit a total of 120 participants in expectation to afford a final sample size of at least 48 in each group (using a conservative estimate of 80% retention). Eligible and willing participants will be randomized to treatment assignment (ESTIMA or wait-list control group) using a randomizer software package, after enrollment. The microfinance groups of women (approximately 6-10 per group) will be formed and randomized to intervention or wait-list control condition. The wait-list control group will be provided with referrals to local FSW support organizations, as the standard of care (STI/HIV testing and referrals), and will receive ESTIMA subsequent to the 12 month follow-up data collection. ESTIMA will involve groups of approximately 6-10 women each; groups will initiate once sufficient numbers are enrolled (i.e. groups will be staggered in terms in initiation).

At the point when we have recruited all eligible and interested participants from the parent study (MAPA de Salud, PI: [name], protocol 100148), if we have not obtained at least 120 participants from the parent study, we will follow the same recruitment protocol as the parent study until we obtain at least 60 participants in each group. We will recruit female sex workers aged 18 years old or older in Tijuana, and who meet other eligibility criteria as described in section 10. Recruitment will be conducted by trained study staff who have worked previously for the parent study and who have experience working in these contexts with this population for a number of years. We will follow time-location sampling to ensure a diverse sample – with recruitment venues and the times at which these sites are frequented changing as the study proceeds. With the help of trained study staff, we will update our existing maps of bars, brothels, hotels, alleys and street corners with sex work activity. We may also choose to allow participants of the study to help identify new sites for recruitment as well as to refer potentially eligible FSW who are interested in the study by providing the study phone number. (See section 11 for more details).

**Screener:** Trained outreach workers will follow recruitment procedures and invite women interested in the ESTIMA program to visit the study's offices. The trained outreach worker will go through the informed consent process with all potential participants before screening for eligibility. Please refer to informed consent procedures elsewhere in the research plan for more details regarding the consent process. Women interested in participating after the informed consent process will be invited by the outreach worker to determine if they are eligible to participate via a 10 minute screener. The outreach worker would make a statement which would include the following: "If you are interested in answering some personal questions about your health and behaviors to see if you qualify for this study, you will receive the in-kind equivalent of \$5 USD for being screened. The questions will take approximately 5-10 minutes of your time. Your answers will not be linked with your name and will be kept private". Personal contact information collected during screening will be kept separate from the screener form and will be kept under lock at our offices, accessed only by staff that need the information to set up

appointments. Screening questions include age, agency over earnings, engaging in exchange of sex for money, drugs, goods or shelter; date of last exchange; intention to move in the next year, drug use, and debt. We will add a few non-related 'red herring' questions (e.g. marital status, place of work) to prevent women from guessing eligibility criteria. Screening will take place in a confidential area where the potential participant feels safe to answer freely.

Survey/Specimen Data Collection. The survey is expected to take approximately 45 minutes and approximately 30 minutes for STI/HIV testing; overall, with waiting times, we expect this aspect of study participation to take approximately 90 minutes. For the baseline ESTIMA survey and HIV/STI testing, we will use data collected from the parent study's 18 months follow-up survey and specimen collection. Participants recruited outside of the parent study will be provided with the survey and STI testing, and reimbursed for their time in the amount of \$30 (at baseline and 12 month follow-up) and \$20 at 6 month follow-up (survey but no STI testing). All participants will also complete a 5-10-minute supplemental survey during informed consent or at another time preferred by the participant and will measure greater details on women's alcohol use frequency and experiences of discrimination; these measures were not asked in the parent study survey but will be important to examine in terms of assessing intervention impact. For the ESTIMA 6 month follow-up, we will use survey data collected from the same survey as implemented at baseline (including the additional questions on alcohol use frequency and experiences of discrimination). Final 12 month follow-up for ESTIMA will be conducted independently of the parent study.. (We have budgeted for the costs associated with testing of ESTIMA participants for the 6 and 12 month follow-up, whereas the baseline will be conducted under the parent study. Trained research assistants arrange a follow-up interview time to be conducted at the study office via contact information collected as part of the parent grant. After providing informed consent, participants complete a 60 minute interviewer-administered survey using computer assisted personal interviewing (CAPI) (NOVA software, MD, USA). The survey (and any new items for the ESTIMA project) will be translated into Spanish, back-translated to English and reviewed for accuracy by the bilingual project coordinator and project consultants, who have also reviewed questions for cultural and linguistic appropriateness. Women will be reimbursed \$30 for the survey and testing (at baseline and 12 month follow-up) and \$20 at 6 month follow-up (survey but no STI testing). Data collection interviewers will not be aware of women's treatment assignment. Women who test positive for any HIV/STI test will be provided with appropriate treatment and/or referral to HIV care services. A participant tracking system will be developed during enrollment for the ESTIMA project in order to collect follow-up data (which will take place at the same study office) and kept up to date with information on address, phone number, etc., and all contact attempts. Permission to use different tracking methods (e.g. contacting friends) will be obtained at enrollment and kept current in order for us to collect the additional assessment after participants' involvement in the parent study ends (our 12 month follow-up). A key study aim is to identify retention challenges, which will be monitored quantitatively and qualitatively (Aim 3). Given that we are recruiting from the 18 month follow-up of the parent study, we also expect to recruit women who have a low probability of attrition, given that they were already among those not lost to follow-up for the 18 month data collection of the parent study. While we will use the parent study's 18 month follow-up data, we do not expect to see reductions in our outcome measures of interest until 12 months follow-up. However, 6 month follow-up may be useful to conduct mediational analyses to understand patterns in or variations of change in the outcome variables.

Outcome Measures. Measures on GBV, gender, HIV, and health were drawn from Demographic Health Surveys (DHS), multiple instruments previously used by investigators, as well as items from the IMAGE study adapted for use in this Mexican context. New items will be added to parent grant surveys (e.g. collective efficacy, additional economic stability variables, women's status indicators) based on Aim 1 findings. Measures will include relevant demographic variables (e.g. age, education, living situation and evictions, other employment, head of household, economic support, number of children). We will include assessments on collective efficacy/power (e.g. perceptions of power in addressing GBV and gender inequity collectively) and women's economic stability using several variables (assessing debts, income, number of sex trades and income from sex trades, other income generating efforts, income independence, economic mobility, self-efficacy and confidence in maintaining financial security, variables measuring consumption-including monies spent on children's needs and education). We will also measure knowledge of gender inequity issues, HIV, and interactions between GBV and HIV, gender equitable attitudes, attitudes around GBV (7 items assessing justification of violence against women), and women's status indicators (including women's economic and social decision-making in household, women's economic mobility, e.g. gender-based challenges in engaging in business or managing finances). GBV will be measured as physical, sexual and psychological acts of violence perpetrated by clients, male partners, and other men in the community, using an internationally adapted Conflict Tactics Scale. Frequency of unprotected sex will be constructed from items assessing the number of times participants had vaginal or anal sex with clients and male partners in the past 90 days and the number of times they used a condom during sex. Measures on alcohol use in the supplemental survey were drawn from recommendations from the World Health Organization and the National Institute on Alcohol Abuse and Alcoholism. Measures on discrimination were adapted from a variety of scales frequently used in social psychology, including the Perceived Discrimination scale and Schedule of Sexist Events scale.

Description of Parent Study Survey (that will be implemented by our study at 6 and 12 months follow-up): Domains are as

follows: Sociodemographics (age, marital status, nationality, place of birth, education, first language, income, employment beyond sex work, family ties, # children and other dependents, living situation, mobility patterns). Financial need is assessed by several items that ask about the participant's earning from sex work, other sources, number of people who are financial dependents, other people who help support the participant and/or her household, whether the participant is in debt and who she owes money to, the nature of relationships with financial dependents, other financial challenges (including housing eviction due to lack of rent money), as well as her interest in future programs to promote women's financial stability. Knowledge of HIV and STIs: General knowledge and attitudes regarding HIV/AIDS and STIs will be assessed through a series of questions (e.g., heard of HIV/AIDS, can list transmission routes and preventive behaviors); Drug use and practices: (age at first use of specific drugs, types of drug used and routes of administration, reasons for drug use, injection drug use (for those injecting, questions on syringe re-use, receptive and distributive syringe sharing, frequency of injection, syringe cleaning, abscesses, sources and cost of syringes, barriers to syringe purchase at pharmacies, shooting gallery attendance, and frequency of arrest and incarceration for charges related to drug possession and paraphernalia will be elicited). FSWs will also be asked to report their use of alcohol and specific drugs preceding and during sex with regular, casual and client partners over the past month; Sexual history and current behaviors: Age at initiation into sex work and current patterns of sex work including number and frequency of unprotected vaginal and anal sex with clients, spouse or steady partner and casual male partners in the past month, number of partners who inject drugs, and use of the male and/or female condoms. Since the proposed study focuses on HIV sexual risk behaviors, we will use the Sexual Relationship Power scale which includes items such as "when you and your partner argue, your partner gets his way most of the time."; Entry into sex work: Women who report underage or forced/coerced entry into sex work will be asked questions regarding entry into sex work and HIV risks during the first 30 days in sex work. These will include place of recruitment, relationship to recruiter, and modes of transportation used, physical and sexual abuse, condom use, coerced/forced drug use, injuries, deprivation of food or clean water, and threats of violence; Second-Generation sex work: including if participants had a parent involved in sex work (i.e. second-generation sex work); Contextual factors include working conditions: work setting (e.g., brothel, street, bar; public vs. isolated), registration status, nature of relationship with pimp or manager (if applicable, including degree of financial independence, control over client selection), degree of protection from drunk or aggressive clients, client characteristics (age, age difference, language, ethnicity, duration of relationship [e.g., stranger], country of origin, demands for unprotected sex, aggression or violence, amount received for protected vs. unprotected vaginal and anal sex), availability of condoms and sterile syringes, commodity and value exchanged. We will also ask about interactions with the legal system including arrest history and reasons, incarceration, current interactions with police. Mental Health, including exposure to violence, will be assessed by a number of scales. *Depressed mood* will be assessed using the 21-item Beck Depression Inventory. Questions on community violence scale developed by Steve and O'Donnell (e.g. hearing gunfire, seeing drug deals, witnessing someone being killed) will also be asked. Access to services (past HIV and STI prevention, testing and treatment, drug treatment (e.g. access to methadone maintenance, buprenorphine maintenance, detoxification, social support programs), usage of medical services in the past 6 months, health insurance status and type of insurance (e.g. IMSS)); Changes in the Risk Environment: Specifically, at baseline, women are asked whether the following has increased, decreased or remained the same in the last year: perceived changes in the total number of clients, US clients, other foreign clients, Mexican clients, presence of municipal police, federal police, army; level of community-, cartel- and client-related violence; access to sterile syringes, condoms, HIV/STI testing and drug treatment.

Data Management. Data collected during the additional assessment (12 months follow-up) conducted by our study will be managed in the same way as the parent study. The DMC will be responsible for questionnaire development and coding. Laptops will be used for CAPI data collection using the QDS™ software. Each CAPI interview file will be saved with a name indicating the QDS version, visit month, laptop number, language used (Spanish or English) and date of interview; all computer files in the field will have daily backups. The Project Coordinator will extract and compile CAPI files into QDS warehouses; these encrypted, password protected files will be backed up during the data collection period. Each study participant will be assigned a unique identifier. For confidentiality reasons, no personal information, such as name or address, will be recorded in the surveys. The Project Coordinator who is fluent in both Spanish and English will be responsible for training the site staff to record, extract, and compile data and also for addressing all technical assistance needs. The Project Coordinator will merge all QDS warehouses together, reconcile them into a standard version, and export a final QDS warehouse into SAS or SPSS data sets that are instantly ready to use by any statistical software. Lab data will be received from paper forms and will be entered via SPSS Data Entry Station.™ A clean SPSS data set can be ready for analysis right after the data entry is finished. All lab data will be double entered using the SPSS\_DE double entry mode. To ensure quality of the data collection, the Project Coordinator will make accrual and retention reports, tracking reports and missing data reports at least bi-weekly. All data managed by the Project Coordinator will be backed up daily and password protected.

Quantitative Data Analyses and Power Calculations. Descriptive statistics (means, frequencies etc.) will be examined to characterize and compare the control and intervention participants on various relevant measures (demographics, GBV,

sexual health risk indicators). The distributional properties and reliability of continuously scaled variables will be examined. Effects of the intervention on both intermediate and long-term outcomes (see Figure 1) will be examined using logistic regression analyses for dichotomous variables (e.g. GBV, consistent condom use) and ANCOVA for continuous variables (e.g. collective efficacy scales, income, number of sex trades). Analyses will focus on outcomes at the 12 month follow-up. ANCOVA using ranks will be used to examine outcome variables with non-normal distributions, such as income. While ESTIMA is powered to focus on intermediate outcomes, we will also investigate trends on longer term outcomes as well (Figure 1). We expect low rates of loss to follow-up, as ESTIMA is incorporated into existing *Via* trainings; however, we will track any participants who drop out of the program (Aim 3), as well as loss to follow up. If there is more than a trivial amount of missing data, we will examine whether there are any patterns in missing data by relevant study variables (e.g. violence experiences, demographic characteristics etc). Power calculations were performed using a significance level of 0.05 and 80% retention (n=48 in each group), with focus on **primary intermediate outcome variables** (economic security and collective power variables) (Figure 1). For analysis focused on variables of income and debt, number of sex trades, as well as the scales measuring women's collective power, we will have 80% power to detect a standardized effect size of 0.5, which is considered a moderate effect size based on work from Cohen (1988). We believe that a moderate effect size would be needed in order to ensure that the effect of the intervention is significant for wide-scale adoption and sufficient impact. However, because we will have small numbers for this pilot of the ESTIMA project, we recognize that we may only be able to find trends to report, and which will be used to secure further funds to run a full-scale trial. While we have not powered the trial to detect a significant effect on GBV, HIV risk behaviors, or HIV/STI, we anticipate a trend toward decreased reports of these in the intervention group compared to the control arm. Furthermore, collecting information on GBV, HIV risk, and HIV/STI will also provide information to power a subsequent larger-scale evaluation.

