### **Phase II**

**2. To assess preliminary outcomes of the ESTIMA HIV Prevention Program** Using a two-armed randomized controlled design, we will recruit FSW (n=120, 60 in each arm) who will be randomized to: 1) the ESTIMA intervention (gender equity program and *Via* microfinance program) or 2) a wait-list control group. Women will be part of groups of approximately 10 women each, and each group will be randomized to intervention or control conditions. At 12 months follow-up, we hypothesize that compared to control participants, intervention participants will have: **a)** Significantly greater economic security (e.g. decreased debt, increased income, decreased number of sex trades) and **b)** Significantly greater perceived collective power (i.e. collective efficacy) to address gendered power imbalances within social structures and the community.

**3. To assess feasibility regarding all aspects of implementation, receptivity by participants and staff, and capacity to be maintained by *Via* microfinance efforts** Qualitative focus groups (n=2 or less per intervention group, 10 women per session), individual interviews (approximately 5 per intervention group), and quantitative assessments will be conducted with intervention participants, along with staff feedback via post-training evaluation forms, to inquire about satisfaction with and appropriateness of the program, as well as aspects pertinent to the ethical conduct of the intervention. We will also monitor recruitment, random assignment, adherence to intervention design, retention of participants, contamination across arms, and the incidence of adverse events.

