### Phase II (Aims 2-3)

From the parent study, we will recruit a total of 120 participants in expectation to afford a final sample size of at least 48 in each group (using a conservative estimate of 80% retention). The microfinance groups of women (approximately 10 per group) will be formed and randomized to intervention or wait-list control condition using a randomizer software package, after baseline data collection for ESTIMA. The wait-list control group will be provided with referrals to local FSW support organizations, as the standard of care, and will receive ESTIMA subsequent to the 12 month follow-up data collection. ESTIMA will involve groups of approximately 10 women each; groups will initiate once sufficient numbers are enrolled (i.e. groups will be staggered in terms in initiation).

Additional recruitment, using the same venue-based sampling protocol as the parent study, will be conducted as needed in order to meet final sample size expectations. Briefly, participants will be recruited from areas in which sex work occurs

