In addition to the baseline assessment (which involves a separate survey at baseline for those recruited outside of the parent study and the extraction of data from the parent study 18 month follow-up from those recruited from the parent study), we will ask participants to fill out a supplemental survey (to collect greater detail on alcohol use frequency and experiences of discrimination that is not collected in the parent study survey, but important to measure in terms of the impact of ESTIMA) which will take an additional 5-10-minutes and will be implemented at the time of informed consent or at another time as preferred by the participants. We will collect these additional assessments using the same survey (including these additional measures) at 6 and 12 months follow-up independent of the parent grant. We will also collect these same assessments for those participants recruited outside of the parent study. The assessments will be incorporated into the larger survey for their baseline assessment.

**Participant Follow-up and Tracking:** Similar to the parent study, this last follow-up assessment will also be conducted at the study site. We expect that since we recruited participants at the 18 month follow-up from the parent grant that they may be among those who were most available for follow-up (since they were not lost to follow-up in the parent grant by 18 months). Other important suggestions from the parent grant for ensuring good follow-up include participant reimbursement for participation, a non-coercive approach, and easy access to the clinic for FSWs from their place of work/residence.

1. The participant recruited during baseline will be advised in her first contact that she will be followed for 2 additional follow-up surveys and STI/HIV testing. She will be told that she is expected to undergo an interview and a free gynecological exam and blood test at this visit, similar to how she has participated in the parent study.
2. The participant will also be asked at her first visit to provide us with the name and telephone number of a contact (girlfriend, fellow worker, bar manager) whom we may contact if we have difficulty locating her for this additional survey and STI/HIV testing. We will provide a small reimbursement (in-kind goods valued at \$5) for her to return in between study visits to update or confirm this information.

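### If both recruitment sources are used, nothing in the plan balances or adjusts for source; the resulting chance imbalance could be large if groups are randomised and is small if individuals are

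*Combined protocol and SAP*

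**What the plan says.** **Sources.** Women are recruited from the parent study first. If that gives fewer than 120, Section 9 (Specific Aim 2) says "we will follow the same recruitment protocol as the parent study until we obtain at least 60 participants in each group". Sections 10 and 11 repeat the fallback, also as conditional. Section 8 says the parent study was at first expected to supply the whole sample, which suggests a shortfall but gives no number.

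**How the sources differ.** Parent-study women have been assessed at 6, 12 and 18 months, and their ESTIMA baseline is taken from a parent visit (the 18-month visit in Sections 9 and 11; Section 10 says the 12-month visit). Section 11 provides a "separate survey at baseline for those recruited outside of the parent study". Section 9 expects low attrition because "they were already among those not lost to follow-up for the 18 month data collection of the parent study", and Section 11 argues the same way.

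**Allocation.** Section 11 says the groups "will be formed and randomized to intervention or wait-list control condition using a randomizer software package, after baseline data collection for ESTIMA". Sections 5, 6 and 10 also say that groups are randomised. Section 9 says both that eligible participants are randomised and that groups of about 6-10 are. Section 16 has women randomly assigned as they are recruited, with about 20 needed to yield one intervention group of 10. Section 11 puts all participants through the same randomisation. No stratification, blocking or matching is described; the only stratification mentioned is geographical, in the parent study's sampling.

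**Analysis.** Section 9 plans logistic regression and ANCOVA at 12 months. Recruitment source is not named as a covariate, and retention by source is not a planned report.

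**The concern.** The two sources differ in prior assessment, in selection for staying in follow-up, and in how baseline is obtained. The protocol's own attrition argument implies better retention in one source than in the other. If the arms end up with different shares of each source, those differences enter the arm comparison, and a retention difference by source appears as a loss difference by arm.

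With many independently randomised women, chance would keep the shares close. With 12 to 20 randomised groups it may not. Sources are used in sequence and groups start as they fill, so many groups could come wholly from one source, and an unlucky draw would then move whole groups. No planned adjustment would remove the effect.

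**Working it through.** **The plan's own figures.** Retention: 60 × 0.80 = 48 per arm, matching "final sample size of at least 48 in each group (using a conservative estimate of 80% retention". Section 9 states that "we will have 80% power to detect a standardized effect size of 0.5". With 48 per arm and a 0.5 SD difference, a normal-approximation two-sample calculation gives 79.0% one-sided at 0.05 and 68.8% two-sided. Two-sided ANCOVA reaches 80.2% if the baseline-outcome correlation is 0.49 (an assumption). The 80% can therefore be reproduced under some readings. It is a separate matter, and only the 0.5 SD target is used below, as a yardstick.

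**Number of randomised units.** 120/10 = 12 groups to 120/6 = 20 groups, so 6 to 10 per arm.

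**If groups are randomised.** Assume each group comes from one source, G groups are split equally between arms, and K of them are parent-study groups (K is not in the documents; 25%, 50% and 75% of G are tried). The number x of parent-study groups in one arm is hypergeometric, and the arms differ in source share by |2x − K|/(G/2).

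| G | K | Chance of a difference of 20 points or more |
|---|---|---|
| 12 | 3 or 9 | 2 × 84/924 = 18.2% |
| 12 | 6 | 1 − 400/924 = 56.7% |
| 16 | 4 or 12 | 1 − 5544/12870 = 56.9% |
| 16 | 8 | 1 − 4900/12870 = 61.9% |
| 20 | 5 or 15 | 1 − 128700/184756 = 30.3% |
| 20 | 10 | 1 − 63504/184756 = 65.6% |

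The figures jump because few splits are possible. With G = 12 and K = 3, the best split (2:1) already differs by 1/6 = 17 points, just under the threshold. The mean absolute difference over the table is 16 to 23 points. If each of 12 or 20 groups were allocated by coin flip instead, simulation gives 39% to 50%.

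**If individuals are randomised 60:60, or groups are a random mix of sources.** With 30, 60 or 90 of the 120 women from the parent study, the same calculation on women gives 1.9%, 4.4% and 1.9%. The mean difference is 6 to 7 points.

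**Effect on the arm contrast.** Shift = imbalance × source effect. A 4:2 split of 6 parent-study groups among 12 gives 4/6 − 2/6 = 33 points. The documents give no source effect, so a range is assumed:

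- 0.1 SD: 0.333 × 0.1 = 0.03 SD
- 0.3 SD: 0.333 × 0.3 = 0.10 SD, which is 0.10/0.5 = one fifth of the target effect

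For scale, the unadjusted standard error before any clustering is √(2/48) = 0.204 SD, so 0.10 SD is about half a standard error.

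**After stratifying groups by source, arms kept equal.** With an even number of groups in each source the difference is 0. With odd numbers it is at most one group: 1/6 = 17 points with 12 groups and 1/10 = 10 points with 20. The chance of a difference of 20 points or more falls to 0.

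**The case against.** A reader might infer that the arm comparison is biased. The documents do not support that. Unstratified randomisation is valid, and an uneven draw is part of the estimator's random error. The 0.03 to 0.10 SD shift applies only given an uneven draw and a real source effect, and nothing in the documents estimates that effect on income, debt, sex trades or collective power.

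A reader might also take the 18% to 66% as the trial's risk. It applies only if whole, mostly single-source groups are randomised. Sections 9 and 16 also describe assigning individual women, and then the chance is 2% to 4%. If the batches of about 20 in Section 16 were split one group to each arm, accrual time, and with it source, would be partly balanced already. No such rule is stated, so this cannot be relied on.

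The contrast between sources should not be overdrawn. Venue recruits also complete a survey and STI/HIV testing before they take part, with counselling, and the sampling method, city and screening are similar. What remains is repeated prior assessment and selection for retention. The mix itself is conditional on a shortfall.

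Section 9 does compare the arms descriptively and examines patterns in more than trivial missing data, and retention is monitored under Aim 3. The trial is also a pilot that says it may find only trends. These points lower the stakes. They do not supply balance or adjustment on a variable that is known for every woman.

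**Conclusion.** The point holds as a conditional, inexpensive improvement. If the parent cohort falls short of 120, two sources with different histories and different expected retention enter one randomisation with no balancing and no planned adjustment.

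The exposure is chance imbalance. It is substantial if single-source groups are randomised, and small if individuals are randomised or groups are well mixed. The upper range rests on 12 to 20 equal groups and the assumed source mix; the size of any shift rests on an assumed source effect. The inconsistent unit of randomisation is the more basic gap, because it decides which range applies.

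**What to change.** - State the unit of randomisation once, and make Section 9 (Recruitment and Random Assignment), Section 11 (Phase II) and Section 16 agree.
- Block or stratify the allocation by recruitment source, in order of accrual. If groups are randomised, use each group's predominant source.
- Record source as a baseline variable, include it as a covariate in the Section 9 logistic and ANCOVA models, and report retention by source and arm.
- Limit the low-attrition statements in Sections 9 and 11 to parent-study women.

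The cost is protocol wording, a change to the randomisation list, one degree of freedom for the covariate, and possibly a short wait for a block to fill. Source needs no new data collection, since Section 16 gives women either their parent-study ID or a new one.

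Forming single-source groups and strictly pairing them should stay optional. With 12 groups, a paired group-level analysis has 6 − 1 = 5 degrees of freedom against 12 − 2 = 10 unpaired, and single-source groups make source purely a group-level factor.
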